13.1 Pharmacokinetics

All completed subjects with quantifiable pharmacokinetic (PK) measurements of secukinumab will be included in the pharmacokinetic data analysis. Serum concentrations will be expressed in mass per volume units. All concentrations below the limit of quantification as well as missing data will be labeled as such in the concentration data listings. PK concentrations will be summarized by visit and treatment group. In addition to mean, standard deviation (SD), coefficient of variation (CV), median and quartiles, the geometric mean and geometric coefficient of variation (CV) and n(log) will be presented. The formula for deriving the geometric mean and CV (%) is as following:

- $CV (\%) = (SD/mean) * 100$,
- $geometric\ mean = \exp(\text{sum of log transformed data} / \text{number of non-missing data points after log transformation})$,
- $geometric\ CV = \sqrt{\exp(\text{variance of log-transformed data}) - 1} * 100$.

In addition, sample number, concentration, sample date, sample time at pre-dose and minutes pre-dose will be listed by treatment sequence.

Values below lower limit of quantification/below detection limit will be imputed by 0.

Pharmacokinetic data of the study treatment will be analyzed with a population-pharmacokinetic mixed effects model. The analysis will be based on a pooled data set, including pharmacokinetic samples from previous studies. The modeling approach will be further detailed in a modeling plan. Results will be reported separately.

14 Safety evaluation

Safety analyses will be done on the safety set.

Summaries will be presented cumulatively from core and extension. For subjects who switched from placebo to secukinumab in core, their data prior to switch will only be reported in in-text tables and listings.

Safety analyses will be performed on treatment received or actual treatment as described below:

The actual treatment or treatment received for summaries of safety data will differ to the treatment assigned at randomization if a subject received the wrong treatment during the core and extension study or if the subject up-titrated to a higher dose.

Subjects who switch treatment during the study (e.g. from placebo to active treatment, or had dose escalation) will be counted to both groups using the appropriate start and stop exposure date.

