5.5.11 Study completion and post-study treatment

A subject will be considered to have completed the study if he/she received treatment for 260 weeks in the combined core study and extension study (last dose being administered at Week 256) and upon completion of the scheduled study assessments and procedures up to and including Visit F268.

Information on the subject's completion or discontinuation of the study and the reason for discontinuation of the study will be recorded on the appropriate Study Phase Completion eCRF page.

A Study Phase Completion evaluation (associated with the last visit of the subject's phase of the study: e.g. Week 156, Week 208 or Week 260) must also be performed when a subject prematurely withdraws from the study for whatever reason. In any case, the investigator or site staff must contact the IRT as soon as possible to record the subject's study completion (Visit F268) and/or discontinuation.

The investigator must provide follow-up medical care for all subjects who are prematurely withdrawn from the study, or must refer them for appropriate ongoing care. This care may include another treatment outside of the study as deemed appropriate by the investigator. This treatment may be any non-biologic DMARD. In case of a biologic treatment, a waiting period of 3 months before initiating the treatment is recommended.

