6.6.2 Pharmacokinetics

Pharmacokinetic (PK) samples will be obtained for all subjects, and secukinumab concentrations will be assessed in serum. The PK samples will be collected pre-dose at scheduled visits as indicated in [Table 6-1](#), [Table 6-2](#) and [Table 6-3](#). The PK Sample Log can be found in the [Appendix 2](#).

All blood samples will be drawn by direct venipuncture in a forearm vein.

The actual sample collection date and exact time will be entered on the PK blood collection summary eCRF. Sampling problems will be noted in the Comments section of the eCRF.

The bioanalyst will provide the samples' concentration data to the team under blinded conditions. The bioanalyst will keep this information confidential until Week 156

PK sample handling, labeling and shipment instructions

Laboratory manuals will be provided by the central laboratory with detailed information on sample collection, sample handling and shipment.

Tubes and labels will be provided by the central laboratory with study/sample type information pre-printed on the label.

Analytical methods

An ELISA method will be used for bioanalytical analysis of secukinumab in serum, with an anticipated lower limit of quantification (LLOQ) of 80 ng/mL. The detailed method description to assess secukinumab concentration will be described in the bioanalytical raw data of the study and in the respective Bioanalytical Data Report (BDR).

7 Safety monitoring

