9.5.4 Pharmacokinetics

All subjects with concentration data will be included in the pharmacokinetic data analysis.

Pharmacokinetic variables

The following pharmacokinetic parameter will be determined: $C_{min,ss}$. $C_{min,ss}$ will be determined using Phoenix software. Individual serum concentrations in $\mu\text{g/ml}$ will be listed. All concentrations below the limit of quantification or missing data will be labeled as such in the concentration data listings. Concentrations below the Limit of Quantification will be treated as zero in summary statistics for concentration data only.

During modeling of the pharmacokinetics of secukinumab, the broad principles outlined in the FDA Guidance for Industry: Population Pharmacokinetics will be followed.

Statistical methods for pharmacokinetic analyses

Summary statistics by visit/time will be provided for the above mentioned parameter and will include arithmetic and geometric means, SD, median, minimum and maximum. Individual concentrations will be listed by subject.

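### SAP 13.1 narrows the PK analysis set to completers with quantifiable levels and does not declare this as a change from the protocol

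*SAP*

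**What the plan says.** Protocol 6.6.2 has PK sampling in everyone: "Pharmacokinetic (PK) samples will be obtained for all subjects, and secukinumab concentrations will be assessed in serum". The assessment schedules and the PK blood log place extension samples at Weeks 156, 208, 260 and 268. Subjects who stop early are asked back 4 weeks after their last dose for the end-of-period assessments, and 12 weeks after it for the follow-up visit. Both visits include a PK sample.

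Protocol 9.5.4 defines who is analysed: "All subjects with concentration data will be included in the pharmacokinetic data analysis". It also gives the below-limit rule: "Concentrations below the Limit of Quantification will be treated as zero in summary statistics for concentration data only".

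SAP 13.1 defines the set differently: "All completed subjects with quantifiable pharmacokinetic (PK) measurements of secukinumab will be included in the pharmacokinetic data analysis". It keeps a zero rule: "Values below lower limit of quantification/below detection limit will be imputed by 0". The denominator of its geometric mean is the "number of non-missing data points after log transformation", and n(log) is reported alongside.

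The SAP does not say what *completed* means for PK, and SAP Section 5 defines no separate PK set. The protocol's definition is in 5.5.11: "A subject will be considered to have completed the study if he/she received treatment for 260 weeks", counted over core and extension together, with assessments finished through the F268 visit. SAP Section 1 undertakes to record departures from the protocol. SAP Section 2 records only one, the removal of multiple imputation and MMRM.

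**The concern.** The SAP adds two conditions that the protocol does not have: finishing the study, and having quantifiable levels. The first is settled after the sample is drawn. On the protocol's definition, whether a Week 156 trough counts depends on what the subject does over the following two years. Protocol 3.1 and 5.5.9 tell investigators to discontinue subjects who do not improve or who worsen, so finishing is linked to response, and response may be linked to exposure. Selecting on such an outcome can distort a summary of troughs by visit.

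The second condition sits awkwardly beside the zero rule, and two programmers could implement the pair differently. What is at stake is the by-visit, by-treatment table of secukinumab concentrations, together with the traceability of a population change that was not declared.

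**Working it through.** The documents state no PK sample size, expected trough or below-limit share, so there is no plan figure to reproduce. The check is a comparison of the texts plus two mean identities.

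**1. Sets compared.** Protocol 9.5.4: any subject with concentration data. SAP 13.1: completed, and with quantifiable measurements. The SAP set is contained in the protocol set and is smaller whenever anyone with PK data stops early or never has a quantifiable level.

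**2. Timing.** Completion under protocol 5.5.11 is established at F268. A Week 156 sample is therefore kept or dropped on events up to 268 − 156 = 112 weeks later, and a Week 208 sample on events up to 268 − 208 = 60 weeks later.

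**3. Completer condition.** Let d be the share of a visit's PK subjects who do not complete, and r their mean trough divided by that of completers. Then

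completer-only mean / all-subject mean = 1 / [(1 − d) + d·r].

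Neither d nor r is in the documents. The low value of d uses the Amendment 1 rationale: 460 enrolled and 432 still on treatment, so (460 − 432)/460 = 28/460 = 6.1%. The other values of d, and all values of r, are assumptions.

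| d | r = 0.5 | r = 0.8 | r = 1.0 | r = 1.2 |
|---|---|---|---|---|
| 6.1% | 1.031 | 1.012 | 1.000 | 0.988 |
| 10% | 1.053 | 1.020 | 1.000 | 0.980 |
| 20% | 1.111 | 1.042 | 1.000 | 0.962 |
| 30% | 1.176 | 1.064 | 1.000 | 0.943 |

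Example: d = 30%, r = 0.5 gives 1/(0.70 + 0.15) = 1.176. The ratio exceeds 1 if leavers have lower troughs and falls below 1 if theirs are higher.

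**4. Quantifiability condition, arithmetic mean.** Let f be the share of subjects at a visit who never have a quantifiable level. Under the zero rule they contribute 0, so the all-subject mean is (1 − f) times the restricted mean, and

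restricted mean / all-subject mean = 1 / (1 − f).

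| f (assumed) | 0 | 0.5% | 1% | 2% | 5% | 10% |
|---|---|---|---|---|---|---|
| ratio | 1.000 | 1.005 | 1.010 | 1.020 | 1.053 | 1.111 |

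The ratio is never below 1. It equals 1 if every dosed subject has at least one value at or above the limit, given in protocol 6.6.2 "with an anticipated lower limit of quantification (LLOQ) of 80 ng/mL".

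**5. Quantifiability condition, geometric mean.** A zero has no logarithm, and the SAP denominator counts only values that survive the log. Zeros are absent under either set, so the ratio is exactly 1.

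**6. The set definition and the zero rule together.** Read per subject, someone with one quantifiable level stays in, and that person's below-limit samples at other visits become 0, so the rule has work to do. Read per sample, every below-limit value is already excluded and the rule never operates. The SAP does not say which is meant.

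**The case against.** The strongest defence is that *completed* is undefined in SAP 13.1 and need not mean 260 weeks of treatment. SAP 17.2 describes the final lock in terms of subjects who finished Week 260, the follow-up visit, or both, and subjects who stop early are also scheduled for that follow-up visit. A reading that keeps many of them is open. This stands as a reason to clarify the text. It does not remove the point, because SAP 8.1 separates those who finish from those who discontinue prematurely, the only explicit definition is in protocol 5.5.11, and the quantifiability condition remains on any reading.

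It is also fair to say that little depends on this table. PK is in neither the primary nor the secondary objectives, nothing is tested, and the population PK model is a separate pooled analysis with its own plan.

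A reader might infer more than the documents support:

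- *That troughs are biased upward.* The completer condition can act in either direction. The quantifiability condition acts only on the arithmetic mean, through an unknown f that may be 0.
- *That the SAP contradicts its own zero rule.* This is so only on the per-sample reading.
- *That zeros vanish unseen from the geometric mean.* The SAP reports n(log) and labels below-limit values in the listings. Treating such values as zero is also the protocol's rule.
- *That the filter compresses a dose difference on which the case against 75 mg rests.* Amendment 1 argues insufficient exposure from ACR, PASI, DAS28 and SF-36 results and cites no concentrations. The documents do not show below-limit values to be commoner at 75 mg.
- *That 28 subjects' Week 156 samples would be lost.* The documents do not say when those subjects left or whether each gave a sample.

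**Conclusion.** The point holds as an undeclared narrowing of the PK set, with an ambiguity in below-limit handling. If completion is taken from protocol 5.5.11, valid Week 156 and Week 208 troughs are excluded on an outcome that follows sampling and may be related to exposure. No single bias figure can be given. Over the assumed ranges (d from 6.1% to 30%, r from 0.5 to 1.2), the completer condition changes the arithmetic mean by a factor of 0.94 to 1.18. Over an assumed f of 0 to 10%, the quantifiability condition changes it by 1.00 to 1.11 and leaves the geometric mean alone. No stated efficacy or safety objective depends on the result, so this is a minor correction, worth making because it costs little and affects the by-visit summaries.

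**What to change.** In SAP 13.1:

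- Define the PK set as all subjects with at least one valid concentration record, counting below-limit results as records, whether or not the subject completed. This restores the protocol's set.
- State that the zero rule applies per sample and in arithmetic summaries.
- Report the number and percentage of below-limit values by visit and actual dose, beside n(log).

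No other substitution for below-limit values is needed; the counts show how many values the geometric mean leaves out.

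If the narrower set is intended, define *completed* and list the change, with its reason, in SAP Section 2.

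The cost is SAP wording and one added line per visit in the PK table. No new data are required. The downside is that reported mean troughs may shift slightly.

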14.1 Adverse events

The crude incidence of treatment emergent adverse events on secukinumab (i.e. events started after the first dose of secukinumab in core study or events present prior to the first dose of secukinumab but increased in severity based on preferred term and within 84 days after last dose of secukinumab) will be summarized by primary system organ class and preferred term for the entire treatment period. Confidence intervals for the crude rate will be derived as described in Section 17.2.3.1 In addition, exposure time-adjusted rates (incidence rate) including 95% confidence intervals will be provided for selected terms for the entire treatment period, (see Section 17.2.4.1) to adjust for differences in exposure.

Adverse events reported will be presented in descending frequency according to its incidence in total secukinumab group (combining all secukinumab treatment groups) starting from the most common event.

Summary statistics will be provided by primary system organ class and preferred term for the entire treatment period for all TEAEs, for serious TEAEs, for possibly related TEAEs, for deaths, for TEAEs causing treatment discontinuation, other serious or clinically significant treatment emergent adverse events or related discontinuations, for TEAEs leading to temporary dose interruptions, for SPP risks and for adjudicated major adverse cardiovascular events (MACE). Separate summaries for adverse events suspected to be related to study drug, will also not be displayed in the current analysis.

TEAEs will also be summarized by primary system organ class and preferred term for the entire treatment period in time segments of 52 and 26 weeks.

Summaries (crude incidence only) will be presented for TEAEs by maximum severity as well. If a particular AE 'severity' is missing, this variable will be listed as missing and treated as missing in summaries.

If a subject reported more than one adverse event with the same preferred term, the adverse event with the greatest severity will be presented. If a subject reported more than one adverse event within the same primary system organ class, the subject will be counted only once with the greatest severity at the system organ class level, where applicable.

When adjudication is required of major cardiovascular events, a summary of those types of events as reported by the investigator and confirmed by adjudication will be provided.

Exposure adjusted incidence rates for TEAEs, selected lower lever risk terms based on TEAEs, serious adverse events, adverse events leading to discontinuation, common AEs (frequency >2% in the Any AIN457 group during the first 24 weeks of treatment or IR > 5/100 subject years during the entire treatment period), SPP risks and MACE will be summarized by primary system organ class and/or by preferred term for the entire period.

The incidence of AEs will be presented per 100 subject years of exposure.

Exposure adjusted incidence rates for TEAEs will also be provided for specific common or very common TEAEs (very common TEAEs are described in the Core Data Sheet).

Adverse events will be reported separately by SMQ according to MedDRA. The MedDRA version used for reporting will be described in a footnote.

Algorithms for date imputations will be provided in the PDS.

The safety analyses that will be performed for treatment emergent AEs, labs, ECG and vital signs for each analysis period is described in table below.

Listings will be provided for all adverse events, all non-fatal serious adverse events, deaths, adverse events leading to discontinuation from study treatment or temporary dose interruption, adverse events by SPP risks and adjudicated MACE events (myocardial infarctions, strokes, and cardiovascular deaths).

For SAEs that occurred during screening a listing will be prepared for all subjects screened including screening failures.

No graphical displays of the crude incidence rates and exposure-adjusted rates will be presented for any AEs and serious AEs by system organ class in the current interim analysis.

An overview of the safety analyses and which will be performed for each analysis period is described in [Table 14-1](#).

Table 14-1 Overview of analyses on some safety endpoints

Analysis period	AEs & SAEs	AEs by severity	Study drug related AEs	AEs-SMQ	Risk	Notables for (vitals/ ECG), lab criteria
Entire Treatment	
 •crude incidence •exposure time adjusted incidence* 	
 •crude incidence 	
 •crude incidence 	
 •exposure time adjusted incidence 	
 •crude incidence •exposure time adjusted incidence 	
 •crude incidence

*Exposure-adjusted incidence rates will be done for the following:

- at the PSOC for AE and SAE
- at the PT level for common AEs, which is defined as at least 2% of the patients in the combined AIN457 groups during the initial treatment period or events that had an incidence rate of at least 5.0 cases per 100 subject-years in the combined AIN457 groups during the entire treatment period
- at Level 1 for Risks and SMQ analyses

For the legal requirements of ClinicalTrials.gov and EudraCT, two required tables on <on-treatment/treatment emergent> adverse events which are not serious adverse events with an frequency greater than 5% and on <on-treatment/treatment emergent> serious adverse events and SAE suspected to be related to study treatment will be provided by system organ class and preferred term on the safety set population.

The tables will include data from the core and the extension part of the trial.

If for a same patient, several consecutive AEs (irrespective of study treatment causality, seriousness and severity) occurred with the same SOC and PT:

- a single occurrence will be counted if there is ≤ 1 day gap between the end date of the preceding AE and the start date of the consecutive AE
- more than one occurrence will be counted if there is > 1 day gap between the end date of the preceding AE and the start date of the consecutive AE

For occurrence, the presence of at least one SAE / SAE suspected to be related to study treatment / non SAE has to be checked in a block e.g., among AE's in a ≤ 1 day gap block, if at least one SAE is occurring, then one occurrence is calculated for that SAE.

The number of deaths resulting from SAEs suspected to be related to study treatment and SAEs irrespective will be included.

14.2 Laboratory data

The summary of lab data will only include on treatment data, which are defined as those lab assessments after the first dose of secukinumab in core and on or before last dose + 84 days.

The summary of laboratory evaluations will be presented for three groups of laboratory tests (hematology, chemistry and urinalysis). In addition to the individual laboratory parameters the ratios “total cholesterol / HDL” and “apolipoprotein B / apolipoprotein A1” will be derived and summarized.

For urinalysis, frequency tables across visits will be presented.

Descriptive summary statistics for the absolute value at study visits as well as the change from baseline to extension study visits will be presented in tabular fashion. These descriptive summaries will be presented by laboratory test and treatment dose. Change from baseline will only be summarized for subjects with both baseline and post baseline values and will be calculated as:

$$\text{change from baseline} = \text{post baseline value} - \text{baseline value}$$

The maximum change (maximum decrease and maximum increase) from baseline for each lab parameter, will also be analyzed. Shift tables will be provided comparing the subject's baseline laboratory evaluation relative to the visit's observed data. For the shift tables, the normal laboratory ranges will be used to evaluate whether a particular laboratory test value was normal, low, or high for each visit value relative to whether or not the baseline value was normal, low, or high. If appropriate, the shifts to the most extreme laboratory test value within a treatment phase (either initial or entire) will be presented as well (including category “high and low”). These summaries will be presented by laboratory test and treatment dose.

Reported laboratory assessments with either a less than or greater than sign (“<” or “>”) will be used for analysis after removal of the sign and conversion to standard unit. These laboratory data will be displayed in listings using the standard unit with the reported sign (“<” or “>”).

The following laboratory parameters will be analyzed with respect to numerical Common Terminology Criteria for Adverse Events (CTCAE) grades, given in [Table 14-2](#): hemoglobin, platelets, white blood cell count, neutrophils, lymphocytes, creatinine, total bilirubin (TBL),

gamma-glutamyl transferase (GGT), alanine aminotransferase (ALT), aspartate aminotransferase (AST), alkaline phosphatase (ALP), glucose, cholesterol, triglycerides (TG).

These summaries will be split into hematology and chemistry for study level reports and the pooled summary of clinical safety.

Shift tables will be presented comparing baseline laboratory result (CTCAE grade) with the worst results (expressed in CTCAE grade) during the treatment phase (either initial or entire) analyzed. Of note, baseline will be defined as last assessment prior to first dosing in the initial treatment phase of the core study. Subjects with abnormal laboratory values will be listed and values outside the normal ranges will be flagged.

Table 14-2 CTCAE grades for laboratory parameters to be analyzed

CTCAE v4.0 Term	Grade 1	Grade 2	Grade 3	Grade 4
HGB decreased (Anemia)	<LLN – 100 g/L	<100 – 80 g/L	<80 g/L	Life-threatening consequences; urgent intervention indicated
Platelet count decreased	<LLN – 75.0 x10e9 /L	<75.0 - 50.0 x10e9 /L	<50.0 – 25.0 x10e9 /L	<25.0 x 10e9 /L
White blood cell decreased	<LLN - 3.0 x 10e9 /L	<3.0 - 2.0 x 10e9 /L	<2.0 - 1.0 x 10e9 /L	<1.0 x 10e9 /L
Neutrophil count decreased	<LLN - 1.5 x 10e9 /L	<1.5 - 1.0 x 10e9 /L	<1.0 - 0.5 x 10e9 /L	<0.5 x 10e9 /L
Lymphocyte count decreased	<LLN - 0.8 x 10e9/L	<0.8 - 0.5 x 10e9 /L	<0.5 - 0.2 x 10e9 /L	<0.2 x 10e9 /L
Creatinine increased*	>1 - 1.5 x baseline; >ULN - 1.5 x ULN	>1.5 - 3.0 x baseline; >1.5 - 3.0 x ULN	>3.0 baseline; >3.0 - 6.0 x ULN	>6.0 x ULN
TBL increased	>ULN - 1.5 x ULN	>1.5 - 3.0 x ULN	>3.0 - 10.0 x ULN	>10.0 x ULN
GGT increased	>ULN - 2.5 x ULN	>2.5 - 5.0 x ULN	>5.0 - 20.0 x ULN	>20.0 x ULN
ALT increased	>ULN - 3.0 x ULN	>3.0 - 5.0 x ULN	>5.0 - 20.0 x ULN	>20.0 x ULN
AST increased	>ULN - 3.0 x ULN	>3.0 - 5.0 x ULN	>5.0 - 20.0 x ULN	>20.0 x ULN
ALP increased	>ULN - 2.5 x ULN	>2.5 - 5.0 x ULN	>5.0 - 20.0 x ULN	>20.0 x ULN
Glucose increased (Hyperglycemia)	>ULN - 8.9 mmol/L	>8.9 - 13.9 mmol/L	>13.9 - 27.8 mmol/L	>27.8 mmol/L
Glucose decreased (Hypoglycemia)	<LLN - 3.0 mmol/L	<3.0 - 2.2 mmol/L	<2.2 - 1.7 mmol/L	<1.7 mmol/L
Cholesterol high	>ULN - 7.75 mmol/L	>7.75 - 10.34 mmol/L	>10.34 - 12.92 mmol/L	>12.92 mmol/L
Hypertriglyceridemia	1.71 - 3.42 mmol/L	>3.42 - 5.7mmol/L	>5.7 - 11.4 mmol/L	>11.4 mmol/L

*Note: for “creatinine increased” the baseline criteria do not apply

Summaries for newly occurring or worsening clinically notable lipid abnormalities will also be provided cumulatively for each of the following parameters and categories:

- HDL:
 - ≤LLN
 - <0.8 x LLN
- LDL, cholesterol, triglycerides:
 - ≥ULN
 - >1.5 x ULN
 - >2.5 x ULN

Newly occurring or worsening liver enzyme abnormalities will also be summarized based on the event criteria given in [Table 14-3](#):

Table 14-3 Liver-related events

Parameter	Criterion
ALT	>3xULN; >5xULN; >8xULN; >10xULN, >20xULN
AST	>3xULN; >5xULN; >8xULN >10xULN; >20xULN
ALT or AST	>3xULN; >5xULN; >8xULN >10xULN; >20xULN
TBL	>1.5xULN, >2xULN, >3xULN,
ALP	>2xULN, >3xULN. >5xULN
ALT or AST & TBL	ALT or AST >3xULN & TBL >2xULN; ALT or AST >5xULN & TBL >2xULN; ALT or AST >8xULN & TBL >2xULN; ALT or AST >10xULN & TBL >2xULN
ALP & TBL	ALP >3xULN & TBL >2xULN ALP >5xULN & TBL >2xULN
ALT or AST & TBL & ALP	ALT or AST >3xULN & TBL >2xULN & ALP <2xULN (Hy's Law) Note: elevated ALP may suggest obstruction as a consequence of gall bladder or bile duct disease; ALP may also be increased in malignancy. FDA therefore terms Hy's Law cases as indicators of pure hepatocellular injury . This does not mean that cases of ALT or AST >3xULN & TBL >2xULN & ALP ≥2xULN may not result in severe DILI.

Notes: 1) In studies which enroll subjects with pre-existing liver disease, baseline LFT may be increased above ULN; in such a case it is meaningful to add the condition “and worse than baseline” to the abnormality criteria

For a combined criterion to be fulfilled, all conditions have to be fulfilled on the same visit. The criteria are not mutually exclusive, e.g. a subject with ALT = 6.42xULN is counted for ALT >3xULN and ALT >5x ULN.

Individual subject laboratory data listings will be provided for all subjects as well as for subjects with newly occurring or worsening CTCAE grades, or with newly occurring or worsening after baseline abnormalities in lipid parameters, or with newly occurring or worsening after baseline abnormalities in liver enzymes.

No box plots over time or other graphs will be presented for any of the laboratory parameters.

